**Table 6-4 Recommended Dose Modifications of Lutathera for Adverse Events**

| Adverse Reaction | Worst Toxicity CTCAE Grade (unless otherwise specified)   | Dose Modification  |
|------------------|---|--|
| Thrombocytopenia | First occurrence of:
Grade 2 (PLT < 75 - 50 x 10  /L)
Grade 3 (PLT < 50 - 25 x 10  /L)
Grade 4 (PLT < 25 x 10  /L) | Withhold dose until complete or partial resolution (Grade 0 to 1).

Resume Lutathera at 3.7 GBq (100 mCi) in patients with complete or partial resolution. If reduced dose does not result in Grade 2, 3 or 4 thrombocytopenia, administer Lutathera at 7.4 GBq (200 mCi) for next dose. |
|                  | Recurrent Grade 2, 3 or 4   | Permanently discontinue Lutathera.   |
| Anemia           | First occurrence of:
Grade 3 (Hgb < 8.0 g/dL); transfusion indicated
Grade 4 (life threatening consequences)  | Withhold dose until complete or partial resolution (Grade 0, 1, or 2).

Resume Lutathera at 3.7 GBq (100 mCi) in   |

| Adverse Reaction | Worst Toxicity CTCAE Grade (unless otherwise specified)  | Dose Modification  |
|------------------|--|--|
|                  |  | patients with complete or partial resolution. If reduced dose does not result in Grade 3 or 4 anemia, administer Lutathera at 7.4 GBq (200 mCi) for next dose.   |
|                  | Recurrent Grade 3 or 4   | Permanently discontinue Lutathera.   |
| Neutropenia      | First occurrence of:
Grade 3 (ANC < 1.0 - 0.5 x 10  /L)
Grade 4 (ANC < 0.5 x 10  /L)   | Withhold dose until complete or partial resolution (Grade 0, 1, or 2).

Resume Lutathera at 3.7 GBq (100 mCi) in patients with complete or partial resolution. If reduced dose does not result in Grade 3 or 4 neutropenia, administer Lutathera at 7.4 GBq (200 mCi) for next dose.       |
|                  | Recurrent Grade 3 or 4   | Permanently discontinue Lutathera.   |
|                  | Defined as:
First occurrence of:

Creatinine clearance less than 60 mL/min; calculate using Cockcroft Gault with actual body weight, or

40% increase in baseline serum creatinine, or

40% decrease in baseline creatinine clearance; calculate using Cockcroft Gault with actual body weight. | Withhold dose until complete resolution.

Resume Lutathera at 3.7 GBq (100 mCi) in patients with complete resolution. If reduced dose does not result in renal toxicity, administer Lutathera at 7.4 GBq (200 mCi) for next dose.  |
| Renal Toxicity   | Recurrent renal toxicity as described above  | Permanently discontinue Lutathera.   |
|                  | Defined as:
First occurrence of:

• Bilirubinemia >3 times the upper limit of normal (Grade 3 or 4), or

• Hypoalbuminemia less than 30 g/L with a decreased prothrombin ratio less than 70%.

   | Withhold dose until complete or partial resolution (Grade 0, 1 or 2).

Resume Lutathera at 3.7 GBq (100 mCi) in patients with complete or partial resolution. If reduced Lutathera dose does not result in G3 or 4 bilirubinemia, administer Lutathera at 7.4 GBq (200 mCi) for next dose. |
|                  | Recurrent hepatotoxicity   | Permanently discontinue Lutathera.   |

| Adverse Reaction                                    | Worst Toxicity CTCAE Grade (unless otherwise specified) | Dose Modification   |
|---|---|---|
| Any other CTCAE* Grade 3 or Grade 4 AE  | First occurrence of:
Grade 3 or 4                    | Withhold dose until complete or partial resolution (Grade 0 to 2).

Resume Lutathera at 3.7 GBq (100 mCi) in patients with complete or partial resolution. If reduced dose does not result in Grade 3 or 4 toxicity, administer Lutathera at 7.4 GBq (200 mCi) for next dose. |
|   | Recurrent Grade 3 or 4                                  | Permanently discontinue Lutathera.  |

 No dose modification required for hematological toxicities Grade 3 or Grade 4 solely due to lymphopenia

\*CTCAE: Common Terminology Criteria for Adverse Events, National Cancer Institute

In addition,

- permanently discontinue treatment with Lutathera if hypersensitivity due to the active substance or any of the excipients of Lutathera is observed;
- temporarily discontinue treatment with Lutathera, until resolution or stabilisation before treatment can be resumed:
  - Occurrence of an intercurrent disease (e.g. urinary tract infection);
  - Major surgery: wait 12 weeks after the date of surgery, then restart the treatment with Lutathera.

If a patient experiences DMT during Lutathera therapy, subsequent treatments with Lutathera are permissible, provided the DMT resolves within 16 weeks following the non-tolerated administration. After resolution of a DMT, a patient may receive subsequent planned treatment(s) at 50% of the standard treatment dose, if this is felt to be safe for the patient, or the risk-benefit assessment is favourable. If the same DMT recurs after treatment with the reduced Lutathera dose, no further Lutathera treatment will be given. If the DMT event does not reoccur, the next treatment is at full dose, if it is considered to be safe for the patient, or the risk-benefit assessment is favourable.

Dose modification recommendations for toxicities might be overruled by dose modification recommendations based on dosimetry, and vice versa, i.e. a dose modification should be applied based on toxicity grading, even if dosimetry values are within limits.

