### 6.5.1.1 Dose modifying toxicities (DMTs)

Management of severe or intolerable adverse drug reactions may require temporary dose interruption, extending the dosing interval from 8 weeks up to 16 weeks, dose reduction, or discontinuation of treatment with Lutathera.

For patients who do not tolerate the protocol-specified dosing schedule, dose adjustments are permitted to allow the patient to continue the study treatment.

The criteria for dose modifications of Lutathera for toxicities are outlined in [Table 6-4](#). The evaluation for potential DMTs will be done by Investigator based on local laboratory results from hematology and biochemistry tests done after each Lutathera treatment.

If a patient requires a dose delay of > 16 consecutive weeks of Lutathera from the intended day of the next scheduled dose, then the patient should be discontinued from the study treatment. In exceptional situations, if the patient is clearly benefitting from the study treatment (i.e. stable disease, partial response, complete response), and in the opinion of the investigator no safety concerns are present, after discussion with Sponsor Medical Monitor and/or DSMB, the patient may remain on the study treatment.

For each patient, a maximum of one dose reduction will be allowed after which the patient will be discontinued from the study.

All dose changes must be recorded on the appropriate electronic case report form (eCRF).

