### 6.5.1.2 Dose modification based on dosimetry

Patients will have bone marrow and kidney dosimetry (as well as that in other organs) determined following the first treatment using planar imaging and blood clearance (for bone marrow) data. In the exceptional circumstances when dosimetry cannot be done in a particular patient after the first dose, it should be done as soon as feasible upon a later dose.

As discussed in [Section 4.2](#), the dosimetry reference limits are 2 Gy and 29 Gy based on bone marrow and kidney dosimetry, respectively.

Dosimetry data will be analysed by a central lab in an expedited manner, and the result of cumulative radiation dose will be provided to the Investigator for each patient to confirm that

the cumulative absorbed dose for subsequent treatments does not exceed the reference limits indicated above for kidney and bone marrow absorbed radiation doses.

For each patient, the Investigator will receive the results of dosimetry analysis (cumulative radiation dose) before the administration of next Lutathera dose (i.e. before the 2nd Lutathera administration if the dosimetry is done after the 1st dose). In parallel, the Investigator will assess safety data for potential DMTs as described in the [Section 6.5.1.1](#) based on local laboratory test results.

In case that the resulting cumulative radiation dose is within the reference limits specified above, and no DMT criteria are met, the Investigator can administer full Lutathera dose for the next administration. DSMB does not need to be consulted in such case.

In case that the resulting cumulative radiation dose (calculated based on dosimetry analysis) exceeds the reference limits specified above, the DSMB will evaluate the totality of dosimetry, PK and safety data (See [Section 8.3](#) and [Section 8.4](#) ) to assess benefit risk for the patient and advise on whether dosing can continue and at which level. In such cases, the Investigator will be informed of the DSMB recommendation (including documented justification based on all data reviewed) prior to the next Lutathera administration. The ultimate decision on dose modification in such cases will remain with the Investigator.

The detailed guidance on dosimetry assessments will be provided in the dosimetry and imaging manuals. The detailed guidance for assessment of patient data and decision-making process for DSMB will be provided in the DSMB charter.

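### Table 6-4, hepatic row: the return-to-7.4 GBq clause tests only one of the row's two toxicity criteria, so one recurrence pattern meets both the full-dose and the stop instruction

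*Protocol*

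**What the plan says.** Protocol Section 6.5.1.1 sends the investigator to Table 6-4 for dose changes after toxicity. Each row has a trigger, a rule for withholding and resuming at 3.7 GBq, a condition for returning to 7.4 GBq, and a line that ends treatment on recurrence.

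The hepatic row has two triggers joined by *or*. The first is bilirubin above 3 times the upper limit of normal (Grade 3 or 4). The second is "Hypoalbuminemia less than 30 g/L with a decreased prothrombin ratio less than 70" per cent. Its return clause reads "If reduced Lutathera dose does not result in G3 or 4 bilirubinemia, administer Lutathera at 7.4 GBq (200 mCi) for next dose". Its stop line is "Recurrent hepatotoxicity", paired with permanent discontinuation.

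The renal row also has several triggers: low creatinine clearance, a 40% rise in serum creatinine, or a 40% fall in creatinine clearance. Its return clause covers all three: "If reduced dose does not result in renal toxicity, administer Lutathera at 7.4 GBq (200 mCi) for next dose". Its stop line refers back to the definition in the row.

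Three rules outside the table bear on the same decision:

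- Text after Table 6-4 (Section 6.5.1.1): "If the same DMT recurs after treatment with the reduced Lutathera dose, no further Lutathera treatment will be given". If the event does not recur, the next treatment is at full dose, but only "if it is considered to be safe for the patient, or the risk-benefit assessment is favourable".
- Section 6.5.1.1, before the table: each patient may have at most one dose reduction, and is discontinued after that.
- Section 6.5.1.2: when cumulative dosimetry is within limits "and no DMT criteria are met, the Investigator can administer full Lutathera dose for the next administration".

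**The concern.** The row defines hepatotoxicity by two criteria but asks about only one when deciding whether full activity may be given again. If albumin and prothrombin meet the second criterion after the reduced dose, and bilirubin stays below Grade 3, the row tells the site both to give 7.4 GBq and to stop permanently.

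The table is the part of the protocol a treating site will consult when setting the next dose. The patients are aged 12 to under 18, in what Section 4.4 calls the first prospective study of the drug in these pediatric populations. A dosing rule for toxicity should give one answer for each laboratory result.

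**Working it through.** The plan states no figure on this point and no calculation applies. The check sets the row's instructions side by side, compares the row with the others, and then asks which instruction the rest of the protocol supports.

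**Step 1. What the hepatic row says after a first hepatic event and one dose at 3.7 GBq.**

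| Finding at 3.7 GBq | Return clause met? | Stop line met? |
|---|---|---|
| Neither criterion | Yes | No |
| Grade 3/4 bilirubinemia only | No | Yes |
| Both criteria | No | Yes |
| Albumin/prothrombin criterion only | **Yes** | **Yes** |

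The first three lines give one answer each. The fourth gives two opposite answers.

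**Step 2. Is this peculiar to the hepatic row?**

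| Row | Trigger | Return to 7.4 GBq requires absence of | Match |
|---|---|---|---|
| Thrombocytopenia | Grade 2, 3 or 4 | Grade 2, 3 or 4 | Yes |
| Anemia | Grade 3 or 4 | Grade 3 or 4 | Yes |
| Neutropenia | Grade 3 or 4 | Grade 3 or 4 | Yes |
| Renal | Any of three criteria | Renal toxicity (all three) | Yes |
| Hepatic | Either of two criteria | Grade 3/4 bilirubinemia only | **No** |
| Any other Grade 3/4 event | Grade 3 or 4 | Grade 3 or 4 | Yes |

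Five of six rows match. The hepatic row is the exception, and its stop line also lacks the reference back to the row's definition that the renal row has.

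**Step 3. Which of the two instructions does the rest of the protocol support?**

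*First event included the albumin/prothrombin criterion, and it recurs.* The same dose-modifying toxicity has recurred, so the text after the table ends treatment.

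*First event was on bilirubin alone, then the albumin/prothrombin criterion is met at 3.7 GBq.* There are two ways to classify this.

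- As recurrent hepatotoxicity: the stop line applies.
- As a new first occurrence: the row would call for withholding and then resuming at 3.7 GBq. That would be a second reduction, which Section 6.5.1.1 does not allow.

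Neither classification leads to 7.4 GBq. Section 6.5.1.2 points the same way, because its permission for full dose assumes that no toxicity criterion is met, and here one is.

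**Result.** The contradiction is confined to the fourth line of Step 1. In every version of that case the surrounding text is against 7.4 GBq, so the error lies in the return clause and not in the stop line.

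**The case against.** The best defence is that no careful site would be misled. The stop line is the next line of the same row. The text after the table ends treatment on recurrence and makes any return to full dose a matter of safety or risk-benefit judgment. Section 8.4.6 requires all earlier safety laboratory results to be evaluated before each administration, and Section 9.1.1 obliges the investigator to stop treatment that would harm the participant. The table itself is headed as recommended modifications. All of this stands, and it is why the point is small. It does not make the clause correct: the defence works only by setting the clause aside.

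A reader might infer that the protocol allows unguarded re-escalation after liver toxicity. It does not, for the reasons just given.

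A reader might also infer that a switch from the bilirubin to the albumin/prothrombin criterion leaves a real gap, because the rule on recurrence speaks of the same toxicity and does not say whether that means the same criterion or the same row. The wording is loose there, but the limit of one dose reduction closes the path to 7.4 GBq on either reading.

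**Conclusion.** The hepatic row of Table 6-4 contradicts itself for one pattern: the albumin/prothrombin criterion met at 3.7 GBq without Grade 3/4 bilirubinemia. The return clause is the faulty text. This is a wording error in a safety dosing rule. It should be corrected, but it does not show that the dosing scheme is unsafe.

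The pattern needs a first hepatic event, resolution, a reduced dose, and then a second event on one particular criterion. I expect that to be rare; this is a judgment, as the documents give no rate. No effect on any endpoint or analysis is claimed. The clause cannot act before the third administration (a full dose, a reduced dose, then the decision), so it does not touch the first-cycle safety endpoint.

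One further inference should not be drawn. Toxicity is evaluated "based on local laboratory results from hematology and biochemistry tests done after each Lutathera treatment", and Table 8-4 lists no prothrombin test, so a reader might conclude that the second criterion cannot be assessed. Section 5.2 already uses prothrombin time at the same albumin limit (3.0 g/dL is 30 g/L), and Section 8.4.6 requires additional specimens after a significant abnormality. The laboratory rows of the assessment schedule in Table 8-2 could not be read and may name the test. The documents do not support a finding there.

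The conclusion rests on the wording of the two triggers, the return clause and the stop line, all of which are legible.

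**What to change.** In the hepatic row of Table 6-4:

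1. In the return clause, replace the condition on Grade 3 or 4 bilirubinemia with *hepatotoxicity as defined above*, and leave the rest of the clause as it is.
2. Change the stop line to *Recurrent hepatotoxicity as described above*.

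Both edits follow the renal row. The fourth case in the working then leads only to discontinuation, and a switch between criteria is covered without having to interpret what counts as the same toxicity.

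Section 14.1 requires a written, approved amendment for any protocol change, so the edits should go into the next one. Amendment 02 already changed this table by adding a footnote. The cost is one clause and a few words, with no new procedure or visit.

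The benefit is limited by timing. Amendment 03 reports 11 patients enrolled by 14 December 2023 and the recruitment target met, so few dosing decisions may remain. Enrolment is stated as at least 8 patients, however, and the cap on PPGL patients was removed, so the documents do not show that dosing has ended.

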### 6.5.1.2 Dose modification based on dosimetry

Patients will have bone marrow and kidney dosimetry (as well as that in other organs) determined following the first treatment using planar imaging and blood clearance (for bone marrow) data. In the exceptional circumstances when dosimetry cannot be done in a particular patient after the first dose, it should be done as soon as feasible upon a later dose.

As discussed in [Section 4.2](#), the dosimetry reference limits are 2 Gy and 29 Gy based on bone marrow and kidney dosimetry, respectively.

Dosimetry data will be analysed by a central lab in an expedited manner, and the result of cumulative radiation dose will be provided to the Investigator for each patient to confirm that

the cumulative absorbed dose for subsequent treatments does not exceed the reference limits indicated above for kidney and bone marrow absorbed radiation doses.

For each patient, the Investigator will receive the results of dosimetry analysis (cumulative radiation dose) before the administration of next Lutathera dose (i.e. before the 2nd Lutathera administration if the dosimetry is done after the 1st dose). In parallel, the Investigator will assess safety data for potential DMTs as described in the [Section 6.5.1.1](#) based on local laboratory test results.

In case that the resulting cumulative radiation dose is within the reference limits specified above, and no DMT criteria are met, the Investigator can administer full Lutathera dose for the next administration. DSMB does not need to be consulted in such case.

In case that the resulting cumulative radiation dose (calculated based on dosimetry analysis) exceeds the reference limits specified above, the DSMB will evaluate the totality of dosimetry, PK and safety data (See [Section 8.3](#) and [Section 8.4](#) ) to assess benefit risk for the patient and advise on whether dosing can continue and at which level. In such cases, the Investigator will be informed of the DSMB recommendation (including documented justification based on all data reviewed) prior to the next Lutathera administration. The ultimate decision on dose modification in such cases will remain with the Investigator.

The detailed guidance on dosimetry assessments will be provided in the dosimetry and imaging manuals. The detailed guidance for assessment of patient data and decision-making process for DSMB will be provided in the DSMB charter.

### **6.5.1.3 Overdose**

Lutathera overdose has a very low probability of occurring since it will be supplied as a single dose "ready to use product" in order to avoid any manipulation outside the production facilities. In addition, the infusion system methods do not allow the concurrent use of two separate Lutathera solution vials. No doubling of the administered radioactivity is ever allowed either in absolute amount or by shortening the time intervals between treatments. Treatments (amount of radioactivity and time of administration) will be monitored during the study and any unallowed treatment modification will be considered a major protocol violation.

### **6.5.2 Dose discontinuation**

The discontinuation of treatment with Lutathera is not a reason for patient's withdrawal from the study (reasons for the patient's withdrawal are discussed in [Section 9](#)). In case of a patient's withdrawal from the study treatment (based on either the patient's or the Investigator's decision), patients will undergo all exams scheduled for the End of Treatment (EoT) visit ([Table 8-2](#)) and continue into the Follow-up period.

If the treatment discontinuation occurs because of laboratory abnormality, or any evidence of toxicity, the Investigator will collect additional specimens for repeat or additional analyses, at intervals appropriate to the abnormality. The patient will be closely followed until sufficient information is obtained to determine the cause or the value regresses. Appropriate remedial measures should be taken and the response recorded in the eCRF.

## **6.6 Additional treatment guidance**

### **6.6.1 Treatment compliance**

Patients will be administered the infusions of Lutathera and amino acid during the clinical trial visit at the site. For each single dose of Lutathera a deviation of  $\pm 10\%$  from the scheduled dose is allowed. All study treatment dispensed must be recorded in the Drug Accountability Log.

### **6.6.2 Recommended treatment of adverse events**

For the treatment and prevention of nausea and vomiting with antiemetics see [Section 6.1.2](#).

Crises due to excessive release of hormones or bioactive substances may occur following treatment, therefore, observation of patients by overnight hospitalization should be considered in both GEP-NET and PPGL cohorts.

Recommended treatments of patients with GEP-NET hormonal crises are: i.v. high dose somatostatin analogues, i.v. fluids, corticosteroids, and correction of electrolyte disturbances in patients with diarrhea and vomiting.

In PPGL cohort, the treatment of symptoms related to catecholamine release should be done as per standard local practice and physician judgment (see [Section 4.5](#)).

Medication used to treat adverse events (AEs) must be recorded on the appropriate CRF.

## **6.7 Preparation and administration of Lutathera and sterile amino acid solution**

Further to patient screening and drug ordering by the site staff, Lutathera solution is supplied as a ready-to-use radiopharmaceutical solution for infusion. Each dose is infused over 30 minutes. There is no need for the patient to fast before treatment. For the detailed administration instructions, refer to the Pharmacy Manual.

The total amount of administered radioactivity has to be determined by measuring the radioactivity in the Lutathera vial before and after administration (the procedure is provided in the pharmacy manual).

All patients will receive concomitant sterile 2.5% Lys-Arg solution for kidney protection (see [Section 6.1.2](#)). The sterile amino acid solution and Lutathera are administered in parallel by peripheral vein infusion at a constant infusion rate through pumps or any other infusion system. The infusion with amino acids starts 30 minutes before the start of Lutathera infusion and continues for a total of 4 h (extension up to 6 h is allowed in case of adverse reactions that require interruption of infusion or slowing the infusion rate). During amino acid infusion patient is allowed to void.

Infusion rates are listed in [Table 6-5](#).

